10.62 All other AEs

Submit via appropriate MCCC Case Report Forms (i.e., paper or electronic, as applicable) the following AEs experienced by a patient and not specified in Section 10.6:

10.621 Grade 1 and 2 AEs deemed *possibly, probably, or definitely* related to the study treatment or procedure.

10.622 Grade 3 and 4 AEs regardless of attribution to the study treatment or procedure.

10.623 Grade 5 AEs (Deaths)

10.6231 Any death within 30 days of the patient’s last study treatment or procedure regardless of attribution to the study treatment or procedure.

10.6232 Any death more than 30 days after the patient’s last study treatment or procedure that is felt to be at least possibly treatment related must also be submitted as a Grade 5 AE, with a CTCAE type and attribution assigned.

**11.0 Treatment Evaluation/Measurement of Effect**

Effect of nasal preparation will be measured by differences in reported nasal symptoms before and after, utilizing responses to questionnaires in Appendix 1 and 2.

**12.0 Descriptive Factors**

12.1 Prior different treatments tried for nose symptoms: 0 vs 1 vs 2 vs 3+

**13.0 Treatment/Follow-up Decision at Evaluation of Patient**

13.1 Ineligible

A patient is deemed *ineligible* if after registration, it is determined that at the time of registration, the patient did not satisfy each and every eligibility criteria for study entry. If the patient received treatment, the patient may continue treatment at the discretion of the

physician as long as there are not safety concerns. The patient will continue in the Active Monitoring/Treatment phase of the study, as per section 4.0 of the protocol.

- If the patient never received treatment, on-study material must be submitted.

### 13.2 Major violation

A patient is deemed a *major violation*, if protocol requirements regarding treatment in cycle 1 of the initial therapy are severely violated that evaluability for primary end point is questionable. If the patient received treatment, the patient may continue treatment at the discretion of the physician as long as there are not safety concerns. The patient will continue in the Active Monitoring/Treatment phase of the study, as per section 4.0 of the protocol.

### 13.3 Cancel

A patient is deemed a *cancel* if he/she is removed from the study for any reason before any study treatment is given. On-study material and the End of Active Treatment/Cancel Notification Form must be submitted. No further data submission is necessary.

## 14.0 Body Fluid Biospecimens: None

## 15.0 Drug Information

### 15.1 Rose Geranium Extract (genus *Pelargonium*) in Sesame Oil Nasal Spray

15.11 **Background:** Rose geranium in sesame oil nasal spray is a compounded product utilizing essential rose geranium oil and sesame oil.

15.12 **Formulation:** We will obtain Rose Geranium from Professional Compounding Centers of America (PCCA).

0.2 mL of Rose Geranium oil will be mixed with 119.8 mL of Sesame Oil. After mixing the compounded product will be aliquoted into nasal spray bottles (30 mL / bottle). The study agent will be compounded by Gateway Pharmacy (Bismarck, ND).

The lot number of all components used per batch of agent will be recorded on a Formula Worksheet (Each batch will be assigned a unique log number on the day the compound is mixed).

The nasal spray containers with screw cap closure will be purchased from Professional Compounding Centers of America (PCCA). The contents of each container will be 30 ml.

Each spray will deliver about 0.1ml of drug to the patient.

15.13 **Preparation and storage:** The rose geranium in sesame oil should be stored in its original closed container at room temperature 20°C to 25°C (68°F to 77°F). Excursions are permitted between 15°C to 30°C (59°F to 86°F) and protected from light.

15.14 **Administration:** Instill 1 spray into each nostril twice daily. One additional spray can be administered if the first spray is not a full spray.

15.15 **Pharmacokinetic information:** None available.

15.16 **Potential Drug Interactions:** None

15.17 **Known potential toxicities:** Lipoid pneumonia (rare).

15.18 **Study agent procurement:**

Gateway Pharmacy (Bismarck, ND) will supply Rose Geranium Oil Nasal Spray to the registered sites participating on the trial.

Mayo and each participating MNCCTN site will order a starter supply of blinded Rose Geranium in Sesame Oil Nasal Spray/Placebo and open label supply from Gateway Pharmacy. Fax the Drug Order Form to:

Gateway Pharmacy  
Bismarck, ND  
[contact]  
[contact]

Registration Office personnel will monitor the supply of blinded Rose Geranium in Sesame Oil Nasal Spray/Placebo at each participating site and will coordinate with Gateway Pharmacy to send additional supplies to sites as needed.

*Outdated or remaining drug/product should be destroyed on site.*

15.19 **Nursing Guidelines:**

1. Warn patients to avoid contact with the eyes as this can cause eye irritation.
2. When applied nasally, patients may experience a bad taste
3. Instruct patients to report any rash or burning with application
4. Agent should be stored at room temperature

15.2 **Placebo**

A matching isotonic nasal saline spray will be identical in appearance to the Rose Geranium Oil Nasal Spray. The isotonic nasal saline spray will contain 0.9% Sodium Chloride. It will also contain 0.133% of benzalkonium chloride solution 50% per 100ml of normal saline, as a preservative. The nasal spray containers with screw cap closure will be purchased from Professional Compounding Centers of America (PCCA). The contents of each container will be 30 ml. The placebo spray should be stored at controlled room temperature (20°-25 ° C or 68°-77° F), with excursions to 15-30°C (59-86°F) permitted.

15.21 **Optional crossover phase:** Patients initially enrolled on the placebo arm have the option to crossover and receive 2 weeks of the Rose Geranium Oil Nasal Spray.

## 16.0 Statistical Considerations and Methodology

16.1 Study Design

This is a randomized, double-blinded, controlled study to determine the ability of rose geranium in sesame oil nasal spray to alleviate nasal vestibulitis in patients undergoing systemic, antineoplastic therapy when compared with isotonic nasal saline. Patients will be randomized in a 1:1 ratio to receive either rose geranium in sesame oil nasal spray or isotonic nasal saline. Randomization will be stratified on the basis of sex (female; male), age in years ( $\leq 50$ ;  $> 50$ ), and seasonal allergies and/or asthma (yes; no). To enhance participation, patients who were

assigned isotonic nasal saline have the option to receive rose geranium in sesame oil nasal spray within two weeks after completion of isotonic nasal saline (i.e. provided that they are still receiving chemotherapy at the time of “crossover”) and continue to receive rose geranium in sesame oil nasal spray for two weeks.

### 16.2 Description of Randomization Routine

After a patient is registered they will be assigned to one of the two arms (rose geranium in sesame oil nasal spray; isotonic nasal saline) in a 1:1 ratio utilizing a dynamic allocation algorithm based on the methods by Pocock and Simon (10). The goal of the algorithm is to maintain arm balance with respect to the aforementioned stratification factors. In order to ensure that arm assignment is not deterministic, a level of randomness has been added to the algorithm such that patients will be assigned to the arm that leads to more imbalance 10% of the time. Dynamic allocation is a common approach in cancer clinical trials where we desire arms to be balanced across several prognostic factors. The method is considered robust because it ensures excellent arm balance overall and within the stratification factor levels, even with a large number of stratification factors (11).

### 16.3 Sample Size, Accrual Time, and Study Duration

Based on our clinical experience, we assume that 30% of the patients on the isotonic nasal saline arm will report that the nasal symptom that was most prominent prior to starting the study will be moderately better or very much better 2 weeks after initiation of the nasal spray. We hypothesize that 65% of the patients receiving rose geranium in sesame oil nasal spray will indicate that their most prominent nasal symptom prior to starting the study will be moderately better or very much better 2 weeks after initiation of the nasal spray. This corresponds to an odds ratio of 1 under the null hypothesis and an odds ratio of 4.33 (rose geranium in sesame oil nasal spray / isotonic nasal saline). Using a Fisher’s exact test and testing at a 0.05 two-sided significance level, we will have 85% power to detect this difference if we randomize 80 eligible and evaluable patients on the study. We anticipate that up to 20% of patients will not have met the eligibility criteria and/or not be evaluable for response assessment, and thus the target sample size will be inflated to 106 patients (53 per arm).

Using conservative estimates, we anticipate an accrual rate of 10 patients per month; therefore, to achieve the targeted accrual of 50 patients per arm, we anticipate that the accrual period will be approximately 10 months. Because the patients randomized to receive isotonic nasal saline may elect to receive rose geranium in sesame oil nasal spray for 2 weeks following the 2-week active monitoring phase, the corresponding total study duration will be approximately 11 months.

May, 2022 addendum: This month it became apparent that 6 patients erroneously received the opposite product to which they had been randomized to receive. This was due to a pharmacy error, by the institution that makes the rose geranium in sesame oil and the nasal saline containers. When this pharmacy had prepared a batch of product and sent such to one participating institution, they put nasal saline code numbers on 5 containers of rose geranium in sesame oil and rose geranium in sesame oil code numbers on 5 containers that had nasal saline product. Only 6 of these containers were given to patients. Given this, we plan to increase the accrual number by 6 patients, to a total of 106 patients. The 6 patients that received the wrong treatment will be retained on the study and included in an intent-to-treat analyses (analyzing patients according to the arm in which they were randomized). As sensitivity analyses, we will also perform a per-protocol analysis (analyzing patients according to the treatment they received) and a separate analysis after excluding the 6 patients that received the wrong treatment. The additional 6 accrued patients will assure that there is adequate power for each of these sensitivity analyses.

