### 16.4.2 Analysis Plan for Primary Endpoint

The primary analysis will be based on a modified intention-to-treat (mITT) population, defined as all patients who signed a consent form, met the eligibility criteria, indicated their most bothersome nasal symptom at baseline, completed the patient global impression of change scale 2 weeks after initiating the nasal spray, and were randomized; furthermore, these patients will be analyzed in the arms to which they were randomized.

The number and percentage of patients experiencing a response 2 weeks after initiating the nasal spray will be estimated within each randomized arm and the corresponding two-sided 95% exact (Clopper-Pearson) confidence interval provided. A between-arm comparison of the proportion of patients experiencing a response 2 weeks after initiating the nasal spray will be made using the Fisher's exact test. Statistical significance will be assessed at the 5% level. In addition, the estimated odds ratio with the 95% confidence interval that matches the Fisher's exact test will be provided.

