#### 16.7 Missing Data

Every attempt will be made to obtain complete data for each patient. For the primary endpoint, evaluable patients are defined as patients who indicated their most bothersome nasal symptom at baseline and completed the patient global impression of change scale 2 weeks after initiating the nasal spray. We are targeting 106 patients to obtain 80 eligible and evaluable patients for the primary endpoint. For all other analyses, no missing data will be imputed; all available data will be listed and summarized.

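### Section 16.3 still states 85% power after the bottle swap; with swapped patients analysed as randomised, primary power is about 77–79% at 84 evaluable patients and 72–75% at 80

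*Combined protocol and SAP*

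**What the plan says.** Section 16.3 assumes that 30% of saline patients and 65% of rose geranium patients respond (odds ratio 4.33). With a two-sided Fisher's exact test at 0.05 it states that "we will have 85% power to detect this difference if we randomize 80 eligible and evaluable patients on the study". The number to be randomised now reads: "thus the target sample size will be inflated to 106 patients (53 per arm"). The allowance for loss behind that number is given in these words: "We anticipate that up to 20% of patients will not have met the eligibility criteria and/or not be evaluable for response assessment".

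The May 2022 addendum, in the same section, explains that the compounding pharmacy miscoded five containers of each product. It adds: "Only 6 of these containers were given to patients". On their handling it says: "The 6 patients that received the wrong treatment will be retained on the study and included in an intent-to-treat analyses". Two sensitivity analyses are added, one by treatment received and one without the six. The addendum's only statement about power is: "The additional 6 accrued patients will assure that there is adequate power for each of these sensitivity analyses".

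Section 16.4.2 defines the primary modified intention-to-treat analysis and says "furthermore, these patients will be analyzed in the arms to which they were randomized". Section 16.7 says "We are targeting 106 patients to obtain 80 eligible and evaluable patients for the primary endpoint".

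**The concern.** The 85% was calculated for two arms in which everyone used the assigned spray. Section 16.3 now sets that pre-swap power beside a post-swap sample size. The swapped patients stay in the analysis that decides the trial, and each one pulls the two arm rates together. The addendum's reasoning about six extra patients suits the analysis that drops the six. It does not deal with the analysis that keeps them in the opposite arm.

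This matters because 85% is the only power figure given for the primary analysis. If the primary result narrowly misses while the sensitivity analyses succeed, readers would judge the miss against a power that the analysis did not have. A figure supplied only after the results are known would look like special pleading.

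**Working it through.** **Inputs.** From 16.3: response rates 0.65 and 0.30, two-sided alpha 0.05, Fisher's exact test, up to 20% loss, 106 randomised, six swapped. From 16.4.2: analysis as randomised. From 16.7: 80 evaluable. The plan does not give the split of the six by arm (from 1:5 to 5:1, because at most five containers of each product were miscoded) or how many of the six are evaluable, so both are varied.

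**Step 1: the plan's own figure.** All 2×2 tables were enumerated with binomial outcomes, and the probabilities of those with Fisher p ≤ 0.05 were summed. At 40 per arm with no swaps, power is 85.9%. The stated 85% is correct for undiluted arms.

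**Step 2: sample size.** 80 / (1 − 0.20) = 100, and the addendum's six make 106. Then 106 × 0.80 = 84.8, so 84 evaluable (42 per arm) represents the planned maximum loss. The target of 80 in 16.7 implies 1 − 80/106 = 24.5% loss.

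**Step 3: dilution.** Assume that a swapped patient responds at the rate of the product received. With n per arm and k swapped in each arm:

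- rose geranium arm: [(n − k) × 0.65 + k × 0.30] / n
- saline arm: [(n − k) × 0.30 + k × 0.65] / n

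For n = 42 and k = 3:

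- rose geranium arm: (39 × 0.65 + 3 × 0.30) / 42 = 26.25 / 42 = 62.5%
- saline arm: (39 × 0.30 + 3 × 0.65) / 42 = 13.65 / 42 = 32.5%

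In general the difference is 0.35 × (1 − total swapped / n). This gives 0.35 × 36/42 = 30.0 points at 42 per arm and 0.35 × 34/40 = 29.75 points at 40 per arm, instead of 35.

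**Step 4: primary power after the swap.** Each arm's responder count is the sum of two independent binomials (correctly treated and swapped). Its exact distribution is crossed with the Fisher rejection region.

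| Evaluable per arm | Loss from 106 | No swaps | Six swapped evaluable | Five | Four |
|---|---|---|---|---|---|
| 40 | 24.5% | 85.9% | 72.0% | 74.7% | 77.2% |
| 42 | 21% | 88.6% | 76.7% | 79.1% | 81.3% |
| 43 | 19% | 86.4% | 73.3% | 76.0% | 78.3% |
| 45 | 15% | 88.3% | 76.6% | 79.0% | 81.1% |
| 47 | 11% | 90.4% | 80.3% | 82.4% | 84.3% |
| 50 | 6% | 93.1% | 85.3% | 86.9% | 88.4% |
| 53 | 0% | 93.2% | 85.8% | 87.4% | 88.7% |

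The dip at 43 per arm is the usual saw-tooth of Fisher's test. At 40 and 42 per arm the split of the six changes the result by about 0.1 point or less; at 43 per arm it changes it by about 1 point. With all six evaluable, 85% is first reached at 50 per arm. Going from 80 to 84 evaluable raises power from 72.0% to 76.7%, about 5 points.

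**Step 5: the sensitivity analyses.** These were recomputed for the arm sizes that each split implies.

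- 84 evaluable: by treatment received about 89%. Excluding the swapped patients gives 84–87% if six are evaluable (84.3% at a 3:3 split) and 87–88% if five are.
- 80 evaluable including all six: by treatment received 86–88%, exclusion 81–84% (80.6% at 3:3).

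The addendum's statement about these analyses is therefore broadly right at 84 evaluable.

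**Step 6: discordant results.** In 400,000 simulated trials at 42 per arm with a 3:3 split, the primary analysis was non-significant while both sensitivity analyses were significant in 8.1%.

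**The case against.** The strongest reply is that no figure is miscalculated. The 85% is a design statement for 65% versus 30%, it reproduces, and the dated addendum beneath it discloses the swap and how it is handled. The plan never claims that the extra six restore primary power. That is fair, and it makes this an outdated statement rather than a wrong calculation. It does not make the figure apply to the analysis now planned.

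The second reply is that the low figures are unfavourable cases. The 20% is a ceiling, and 80 of 106 goes beyond it. All six swapped patients need not be evaluable: at 20% loss that has probability 0.8⁶ = 0.26, and four or fewer has probability about 0.34. Averaging over random loss in each arm (53 per arm, 3:3 split, the same loss rate for swapped patients) gives primary power of about 79% at 20% loss, 81% at 15% and 85% at 10%. This also stands: if loss is about 10% or less, 85% is roughly right again. But the plan allows for 20% and names 80 as its evaluable target, and at both the figure fails.

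Third, the saw-tooth means that exact percentages should not be over-read: 85 evaluable gives 75–76% with all six included, slightly less than 84 does. Approximate wording is enough. Fourth, a restated power does not tell a reader how to interpret discordant results. That is true; it only supplies the right planning figure for doing so.

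**Conclusion.** The concern holds. The 85% does not describe the primary analysis after the swap, either at the plan's allowed loss or at its stated evaluable target. Power is about 77–79% at 84 evaluable patients and 72–75% at 80, with six or five swapped patients evaluable. With four it is about 81% and 77%, still short of 85%.

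These figures rest on the plan's own response rates, on swapped patients responding at the rate of the product received, and on equal arms. The unknown split by arm hardly matters at these sizes; the number of swapped patients evaluable does. The as-randomised analysis remains valid and is the proper primary analysis. What needs correcting is the power stated for it.

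**What to change.** Add to 16.3, after the addendum:

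> Assuming swapped patients respond at the rate of the product received, the as-randomised primary analysis has about 77–79% power with 84 evaluable patients (six or five swapped patients evaluable) and about 72–75% with 80; with all six evaluable it returns to 85% at about 100 evaluable. With 84 evaluable, the treatment-received analysis has about 89% and the exclusion analysis about 84–88%; with 80 evaluable including all six, the exclusion analysis has about 81–84%.

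Mark the existing 85% as the design figure before the swap. Once the arm split and the number of swapped patients evaluable are confirmed, the ranges can be narrowed.

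The cost is two sentences and a less favourable stated power. Enrolment, test, population and decision rule do not change.

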## 16.4 Statement for Primary Endpoint

### 16.4.1 Primary Endpoint

The primary endpoint is a binary variable indicating whether the patient achieves a response (yes; no) at 2 weeks after initiating the nasal spray. Response is determined from a patient global impression of change scale and is defined as a patient reporting that the nasal symptom that was most prominent prior to starting the study has been moderately better or very much better 2 weeks after initiating the nasal spray.

### 16.4.2 Analysis Plan for Primary Endpoint

The primary analysis will be based on a modified intention-to-treat (mITT) population, defined as all patients who signed a consent form, met the eligibility criteria, indicated their most bothersome nasal symptom at baseline, completed the patient global impression of change scale 2 weeks after initiating the nasal spray, and were randomized; furthermore, these patients will be analyzed in the arms to which they were randomized.

The number and percentage of patients experiencing a response 2 weeks after initiating the nasal spray will be estimated within each randomized arm and the corresponding two-sided 95% exact (Clopper-Pearson) confidence interval provided. A between-arm comparison of the proportion of patients experiencing a response 2 weeks after initiating the nasal spray will be made using the Fisher's exact test. Statistical significance will be assessed at the 5% level. In addition, the estimated odds ratio with the 95% confidence interval that matches the Fisher's exact test will be provided.

### 16.4.3 Planned Sensitivity Analyses for Primary Endpoint

To assess the robustness of the primary results, a supportive analysis is planned. A logistic regression analysis will be undertaken to estimate the treatment effect after adjusting for the three stratification factors, the corresponding baseline severity for the most prominent nasal symptom, and potential confounding variables. Additionally, the primary analysis will be repeated to include patients who did not complete the patient global impression of change scale 2 weeks after initiating the nasal spray but would otherwise be included in the mITT population. For this analysis, we will assume that the missing values for these patients represent no improvement.

## 16.5 Analysis Plan for Secondary Endpoints

For the most prominent nasal symptom indicated at baseline, patients will record the severity on an ordinal scale of 1=mild, 2=moderate, 3=severe, and 4=very severe. Two weeks after initiating the nasal spray the patients will record the severity of the most prominent nasal symptom as 0=none, 1=mild, 2=moderate, 3=severe, and 4=very severe. A shift table will be created to descriptively display the number of patients who record a 1, 2, 3, or 4 at baseline and the shift two-weeks after initiating the nasal spray. [In addition, the within-patient change in severity of the most prominent nasal symptom will be calculated 2 weeks after initiating the nasal spray and summarized descriptively within each arm. The Wilcoxon rank-sum test will be performed, and the methods of Hodges and Lehmann will be applied to compute a point estimate and confidence interval for the difference in medians between the two arms. As a supportive analysis, the van Elteren statistic, which is an extension to the Wilcoxon rank-sum test that accounts for the stratification factors, will be calculated. Furthermore, we will model the ordinal response data obtained two weeks after initiating the nasal spray with a proportional odds

cumulative logit model; explanatory variables will include arm, corresponding baseline severity for the most prominent nasal symptom, the stratification factors, and other potential confounding variables.

In addition to summarizing the most prominent nasal symptom that the patient indicated at baseline, each nasal symptom (dryness, pain, bleeding, and scabbing) will be descriptively summarized, tabulated, and plotted according to arm at baseline, and at 1 and 2 weeks post-baseline; additionally, we will group patients according to baseline severity for each symptom and summarize changes over time and according to arm. Shift tables will also be generated to descriptively display the number of patients who record a 1, 2, 3, or 4 at baseline and the shift one- and two-weeks after initiating the nasal spray. These analyses are descriptive in nature and are intended to further contextualize the main study findings that are based on analyzing the most prominent nasal symptom reported by the patient.

The constellation of adverse events (AEs) as scored using the National Cancer Institute Common Terminology Criteria for Adverse Events, v5.0 (CTCAE v5.0) will be summarized within arms by reporting the number and percentage of patients. Specifically, to evaluate the AE profiles associated with each arm, the maximum grade for each type of AE will be recorded for each patient and frequency tables will be reviewed to determine overall patterns and compared between arms using Wilcoxon tests.

